6.4 Efficacy

- Assessment of SpondyloArthritis International Society criteria (ASAS)

Term	Percentage
Organic	50
Non-GMO	60
Artificial	70
Natural	75
Organic	78
Artificial	80
Non-GMO	82
Natural	85
Organic	88
Artificial	90
Non-GMO	92
Natural	95
Organic	98
Artificial	99
Non-GMO	100

6.4.1 Assessment of SpondyloArthritis International Society criteria (ASAS)

The ASAS response measures consist of the following assessment domains (Sieper 2009):

Main ASAS domains:

1. Patient's global assessment of disease activity measured on a VAS scale

2. Patient's assessment of back pain, represented by either total or nocturnal pain scores, both measured on a VAS scale
3. Function represented by BASFI average of 10 questions regarding ability to perform specific tasks as measured by VAS scale
4. Inflammation represented by mean duration and severity of morning stiffness, represented by the average of the last 2 questions on the 6-question BASDAI as measured by VAS scale

Additional assessment domains:

5. Spinal mobility measured by BASMI (cervical rotation, maximal intermalleolar distance, spinal lateral flexion, lumbar flexion (modified Schober index), tragus-to-wall distance)
6. C reactive protein (acute phase reactant)

6.4.1.1 ASAS Response Criteria (ASAS 20)

The ASAS Response Criteria (ASAS 20) is defined as an improvement of at least 20% and absolute improvement of at least 10 units on a 0-100 mm scale in at least 3 assessment domains 1 to 4 and no worsening of more than 20% and 10 units on a 0-100 mm scale in the remaining unit.

6.4.1.2 ASAS Response Criteria (ASAS 40)

The ASAS Response Criteria (ASAS 40) is defined as an improvement of at least 40% and absolute improvement of at least 20 units on a 0-100 mm scale in at least 3 assessment domains 1 to 4 and no worsening at all in the remaining domain.

6.4.1.3 ASAS 5/6 improvement criteria

The ASAS 5/6 improvement criteria is an improvement of $\geq 20\%$ in at least five of all six domains.

6.4.1.4 ASAS partial remission criteria

The ASAS partial remission criteria is defined as a value not above 2 units in each of the domains 1 to 4 on a scale of 10.

6.4.1.5 Patient's global assessment of disease activity (VAS)

The patient's global assessment of disease activity will be performed using a 100 mm visual analog scale (VAS) ranging from not severe to very severe, after the question *"How active was your disease on average during the last week?"*.

6.4.1.6 Patient's assessment of back pain intensity (VAS)

The patient's assessment of back pain will be performed using a 100 mm VAS ranging from no pain to unbearable pain, after the question *"Based on your assessment, please indicate what is the amount of back pain at any time that you experienced during the last week?"* and *"Based on your assessment, please indicate what is the amount of back pain at night that you experienced during the last week?"*.

6.4.1.7 Bath Ankylosing Spondylitis Functional Index (BASFI)

The BASFI is a set of 10 questions designed to determine the degree of functional limitation in those subjects with AS. The ten questions were chosen with a major input from subjects with AS. The first 8 questions consider activities related to functional anatomy. The final 2 questions assess the subjects' ability to cope with everyday life. A 0 through 10 scale (captured as a continuous VAS) is used to answer the questions. The mean of the ten scales gives the BASFI score – a value between 0 and 10.

6.4.1.8 Bath Ankylosing Spondylitis Disease Activity Index (BASDAI)

The BASDAI consists of a 0 through 10 scale (0 being no problem and 10 being the worst problem), which is used to answer 6 questions pertaining to the 5 major symptoms of AS:

[figure not shown]
1. Fatigue
2. Spinal pain
3. Joint pain / swelling
4. Areas of localized tenderness (called enthesitis, or inflammation of tendons and ligaments)
5. Morning stiffness duration
6. Morning stiffness severity

[figure not shown]
[figure not shown]
[figure not shown]
To give each symptom equal weighting, the mean (average) of the two scores relating to morning stiffness is taken (questions 5 and 6). The resulting 0 to 10 score is added to the scores for questions 1 through 4. The resulting 0 to 50 score is divided by 5 to give a final 0 – 10 BASDAI score. Scores of 4 or greater suggest suboptimal control of disease, and subjects with scores of 4 or greater are usually good candidates for either a change in their medical therapy or for enrollment in clinical trials evaluating new drug therapies directed at AS. BASDAI is a quick and simple index taking between 30 seconds and 2 minutes to complete.

6.4.1.9 BASDAI 50

BASDAI 50 response is defined as at least a 50% improvement (decrease) in total BASDAI score, as compared to the baseline total BASDAI score ([Braun 2003](#); [Rudwaleit 2004](#)).

6.4.10 Appropriateness of efficacy assessments

The efficacy outcome measures used in this study are the standard measures used across all AS trials and are required for filing.

This study involves exposure to radiation from x-rays of the cervical and lumbar spine. The radiation exposure by these procedures is not necessary for medical care but is intended for research purposes only.

The amount of cumulative *annual* radiation in this study is about 3.42 mSv for the x-ray procedures and is based on effective doses for various diagnostic radiological procedures reported in literature ([Mettler 2008](#)). This exposure is comparable to the natural radiation an average person receives in one year. The radiation between 3 mSv and 50 mSv is considered 'minimal' ([Stabin 2009](#)). Therefore, the radiation exposure in this study involves minimal risk and is necessary to obtain the research information desired.

6.5 Safety

- Physical examination
- Vital signs
- Height and weight
- Electrocardiogram
- Local tolerability (injection site reactions)
- Laboratory evaluations (hematology, clinical chemistry, lipid panel, urinalysis)
- Pregnancy and assessment of fertility

All blood draws and safety assessments should be done prior to study treatment administration. Appropriate safety assessments (e.g. evaluation of AEs and SAEs including injection site reactions) should be repeated after the dose is administered.

6.5.1 Physical examination

A physical examination will be performed at scheduled visits as indicated in [Table 6-1](#), [Table 6-2](#), and [Table 6-3](#). The physical examination will include the examination of general appearance, skin, neck, eyes, ears, nose, throat, lungs, heart, abdomen, back, lymph nodes, extremities, vascular and neurological systems.

Information for all physical examination must be included in the source documentation at the study site. Significant findings that are present before signing the ICF must be included in the relevant medical history eCRF. Significant findings made after signing the ICF which meet the definition of an AE must be recorded in the Adverse Event eCRF.

6.5.2 Vital signs

This will include blood pressure and pulse rate measurements after 5 minutes rest in sitting position.

If possible, vital signs assessments should be performed by the same study site staff member using the same validated device throughout the study.

6.5.3 Height and weight

Body weight (to the nearest 0.1 kilogram [kg] in indoor clothing) (both without shoes) will be measured. The baseline height from the core study will be used in this trial. Therefore, height will not be collected in this trial

If possible, body weight assessments should be performed by the same study site staff member using the same scale throughout the study.

6.5.4 Laboratory evaluations

A central laboratory will be used in this study. All laboratory tests should be conducted at the central laboratory except for [REDACTED] urinalysis/urine pregnancy tests. Details on the collection, shipment of samples and reporting of results by the central laboratory are provided in the laboratory manual. For the identification of clinically notable values, see [Appendix 1](#). All subjects with laboratory tests containing clinically significant abnormal values are to be followed until the values return to normal ranges or until a valid reason, other than treatment related AE, is defined.

6.5.4.1 Hematology

Hemoglobin, platelet, red blood cell (RBC), white blood cell (WBC) and different white blood cell counts will be measured at scheduled visits.

6.5.4.2 Clinical chemistry

Serum chemistries will include glucose, urea, creatinine, total bilirubin, AST (SGOT), ALT (SGPT), GGT, alkaline phosphatase, sodium, potassium, bicarbonate, calcium, phosphorous, total protein, albumin, and uric acid.

6.5.4.3 Lipid panel

A lipid profile including High Density Lipoprotein (HDL), Low Density Lipoprotein (LDL), cholesterol and triglycerides will be measured from a fasting blood sample.

6.5.4.4 Cardiovascular panel

A cardiovascular profile including lipoprotein (a), apolipoprotein B-100, apolipoprotein A-1, and adiponectin will be measured from a blood sample.

6.5.4.5 Urinalysis

Dipsticks will be provided by the central laboratory to the sites for local urinalysis assessments. The urinalysis results for standard parameters such as protein, glucose, blood and WBCs will be recorded in the appropriate eCRF page.

6.5.5 Electrocardiogram (ECG)

A standard 12 lead ECG will be performed as indicated in [Table 6-1](#), [Table 6-2](#), and [Table 6-3](#).

All ECGs must be performed on the ECG machines provided for the study.

All ECGs will be independently reviewed. Instructions for the collection and transmission of the ECGs to the independent reviewer will be provided in the ECG investigator manual.

Clinically relevant abnormalities should be recorded on the relevant medical history/Current medical conditions eCRF page for the baseline ECG.

Clinically relevant abnormalities noted after the baseline ECG should be reported as AE ([Section 7](#)).

6.5.6 Local tolerability (injection site reactions)

The local tolerability at the site of the s.c. injection of the study treatment will be assessed in case of any local reaction, until the reaction has disappeared.

The assessment of pain, redness, swelling, induration, hemorrhage and itching will be performed by a physician and will be recorded on the Adverse Events eCRF, including the severity (mild, moderate, severe) and the duration.

6.5.7 Pregnancy and assessments of fertility

Secukinumab should not be given to pregnant women; therefore effective method of birth control must be used for women of child-bearing potential (see exclusion criteria definitions, [Section 4.2](#)).

All women who are not surgically sterile when enrolling into the study will have local urine pregnancy tests as indicated in [Table 6-1](#), [Table 6-2](#), and [Table 6-3](#). A positive urine pregnancy test requires immediate interruption of study medication until serum β -hCG is performed and found to be negative. If positive, the subject must be discontinued from the trial.

6.5.9 Appropriateness of safety measurements

The safety measures used in this study are reliable and relevant standard measures for a biologic in AS.

7 Safety monitoring

7.1 Adverse events

An adverse event (AE) is any untoward medical occurrence (i.e., any unfavorable and unintended sign [including abnormal laboratory findings], symptom or disease) in a subject or

clinical investigation subject *after providing written informed consent* for participation in the study. Therefore, an AE may or may not be temporally or causally associated with the use of a medicinal (investigational) product.

The occurrence of adverse events should be sought by non-directive questioning of the subject at each visit during the study. Adverse events also may be detected when they are volunteered by the subject during or between visits or through physical examination, laboratory test, or other assessments.

Abnormal laboratory values or test results constitute adverse events only if they fulfill at least one of the following criteria:

- they induce clinical signs or symptoms
- they are considered clinically significant
- they require therapy

Clinically significant abnormal laboratory values or test results should be identified through a review of values outside of normal ranges/clinically notable ranges, significant changes from baseline or the previous visit, or values which are considered to be non-typical in subject with underlying disease. Investigators have the responsibility for managing the safety of individual subject and identifying adverse events. Alert ranges for labs and other test abnormalities are included in [Appendix 1](#).

Adverse events should be recorded in the Adverse Events CRF under the signs, symptoms or diagnosis associated with them accompanied by the following information:

- the severity grade [mild, moderate, severe]
 - mild: usually transient in nature and generally not interfering with normal activities
 - moderate: sufficiently discomforting to interfere with normal activities
 - severe: prevents normal activities
- its relationship to the study treatment (no/yes)
- its duration (start and end dates) or if the event is ongoing an outcome of not recovered/not resolved should be reported.
- whether it constitutes a serious adverse event (SAE)
- action taken regarding study treatment
- whether other medication or therapies have been taken (concomitant medication/non-drug therapy)
- its outcome (not recovered/not resolved; recovered/resolved; recovering/resolving, recovered/resolved with sequelae; fatal; or unknown)

An SAE is any adverse event (appearance of (or worsening of any pre-existing) undesirable sign(s), symptom(s) or medical conditions(s) which meets any one of the following criteria:

- is fatal or life-threatening
- results in persistent or significant disability/incapacity
- constitutes a congenital anomaly/birth defect
- requires inpatient hospitalization or prolongation of existing hospitalization, unless hospitalization is for (*specify what it includes*):
 - routine treatment or monitoring of the studied indication, not associated with any deterioration in condition
 - elective or pre-planned treatment for a pre-existing condition that is unrelated to the indication under study and has not worsened since signing the informed consent
 - treatment on an emergency outpatient basis for an event not fulfilling any of the definitions of a SAE given above and not resulting in hospital admission
 - social reasons and respite care in the absence of any deterioration in the subject's general condition
- is medically significant, i.e. defined as an event that jeopardizes the subject or may require medical or surgical intervention to prevent one of the outcomes listed above.

All malignant neoplasms will be assessed as serious under "medically significant" if other seriousness criteria are not met.

Unlike routine safety assessments, SAEs are monitored continuously and have special reporting requirements; see [Section 7.2](#).

All adverse events should be treated appropriately. Treatment may include one or more of the following: no action taken (i.e. further observation only); investigational treatment dosage adjusted/temporarily interrupted; study drug(s) permanently discontinued; concomitant medication given; non-drug therapy given. The action taken to treat the adverse event should be recorded on the Adverse Event CRF.

Once an adverse event is detected, it should be followed until its resolution or until it is judged to be permanent, and assessment should be made at each visit (or more frequently, if necessary) of any changes in severity, the suspected relationship to the investigational study treatment, the interventions required to treat it, and the outcome.

Information about common side effects already known about the investigational drug can be found in the Investigator Brochure (IB) or will be communicated between IB updates in the form of Investigator Notifications. This information will be included in the subject informed consent and should be discussed with the subject during the study as needed.

The investigator should also instruct each subject to report any new adverse event (beyond the protocol observation period) that the subject, or the subject's personal physician, believes might reasonably be related to study treatment. This information should be recorded in the investigator's source documents; however, if the AE meets the criteria of an SAE, it must be reported to Novartis.

7.2 Serious adverse event reporting

To ensure subject safety, every SAE, regardless of causality, occurring after the subject has provided informed consent and until 12 weeks following the last administration of study treatment or 30 days after the subject has stopped study participation must be reported to Novartis within 24 hours of learning of its occurrence. Any SAEs experienced after this period should only be reported to Novartis if the investigator suspects a causal relationship to study treatment.

Recurrent episodes, complications, or progression of the initial SAE must be reported as follow-up to the original episode, regardless of when the event occurs. This report must be submitted within 24 hours of the investigator receiving the follow-up information. An SAE that is considered completely unrelated to a previously reported one should be reported separately as a new event.

Information about all SAEs (either initial or follow up information) is collected and recorded in English on the paper Serious Adverse Event Report Form or the electronic Serious Adverse Event Form within the OC/RDC system (where available). The Investigator must assess the relationship to each specific component of the study treatment (if the study treatment consists of several components).

SAEs (initial and follow-up) that are recorded *on the paper SAE form* should be faxed within 24 hours of awareness of the SAE to the local Novartis Drug Safety and Epidemiology Department. The telephone and fax number of the contact persons in the local department of Drug Safety and Epidemiology, specific to the site, are listed in the investigator folder provided to each site. The original copy of the SAE Report Form and the fax confirmation sheet must be kept with the case report form documentation at the study site. Follow-up information should be provided using a new paper SAE Report Form stating that this is a follow-up to a previously reported SAE

SAEs (initial and follow-up) that are recorded *electronically* in the OC/RDC system should be entered, saved and e-signed within 24 hours of awareness of the SAE or changes to an existing SAE. These data will automatically be submitted to Novartis Drug Safety & Epidemiology immediately after investigator signature or 24 hours after entry, whichever occurs first.

Follow-up information provided should describe whether the event has resolved or continues, if and how it was treated, whether the treatment code was broken or not and whether the subject continued or withdrew from study participation. Each re-occurrence, complication, or progression of the original event should be reported as a follow-up to that event regardless of when it occurs.

If the SAE is not previously documented in the Investigator's Brochure or Package Insert (new occurrence) and is thought to be related to the investigational treatment a Drug Safety and Epidemiology Department associate may urgently require further information from the investigator for Health Authority reporting. Novartis may need to issue an Investigator Notification (IN) to inform all investigators involved in any study with the same investigational treatment that this SAE has been reported. Suspected Unexpected Serious Adverse Reactions (SUSARs) will be collected and reported to the competent authorities and relevant ethics committees in accordance with Directive 2001/20/EC or as per national regulatory requirements in participating countries.

7.3 Pregnancy reporting

To ensure subject safety, each pregnancy occurring while the subject is on study treatment must be reported to Novartis within 24 hours of learning of its occurrence. The pregnancy should be followed up to determine outcome, including spontaneous or voluntary termination, details of the birth, and the presence or absence of any birth defects, congenital abnormalities, or maternal and/or newborn complications.

Pregnancy should be recorded on a Clinical Trial Pregnancy Form and reported by the investigator to the local Novartis Drug Safety and Epidemiology Department. Pregnancy follow-up should be recorded on the same form and should include an assessment of the possible relationship to the study treatment.

Any SAE experienced during pregnancy must be reported on the SAE Report Form.

8 Data review and database management

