The treatment will be offered in prefilled syringes (PFS) in the extension study. This is a change from the core study, which used s.c. injections prepared from lyophilisate. Subjects will be instructed in detail how to self-administer the s.c. injection using the PFS formulation. Each injection will be administered into an appropriate injection site of the body (thighs, arms, or abdomen). For the first 3 months of the study (through Week 116), all injections will be performed at the study site. Starting on Week 120, the subject is allowed to self-administer the study medication at home or continue to present at monthly intervals to the study site for injection administrations, based on the subject's preference and the investigator's judgment. Site staff will administer the injection to subjects who are not able or unwilling to self-administer the PFS injection.

At Week 156 or after approval and implementation of Protocol Amendment 1, whichever occurs first, site personnel and the subject will be unblinded as to their current treatment regimen. The subject will continue to receive the same dose of secukinumab and will no longer receive the placebo PFS. After approval and implementation of Protocol Amendment 1, the study medication for subjects on the 75 mg treatment arm should be escalated from 75 mg s.c. to 150 mg s.c. every 4 weeks for patients whose overall therapeutic response is not fully achieved with the current dose of 75 mg and may improve with a higher dose, as judged by the investigator. The escalation of the study medication may be determined at any site visit..

[figure not shown]
For patients escalated to secukinumab 150 mg s.c. every 4 weeks, no dose reduction can be performed and if the patient is unable to tolerate the 150 mg dose of secukinumab alternative treatment options should be considered only after discontinuation from the study ([Section 5.5.9](#)).

Assessments for safety, efficacy, [REDACTED] will be performed according to the assessment schedule ([Table 6-1](#), [Table 6-2](#), [Table 6-3](#)).

A follow-up visit is to be done 12 weeks after the last study treatment administration for all subjects (regardless of whether they complete the entire study as planned or discontinue prematurely).

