4.2 Exclusion criteria

Subjects fulfilling **any** of the following criteria are not eligible for inclusion in this study. No additional exclusions may be applied by the investigator, in order to ensure that the study population will be representative of all eligible subjects.

1. History of hypersensitivity to any of the study drugs or to drugs of similar chemical classes
2. Any subject who is deemed not to be benefiting from the study drug based upon lack of improvement or worsening of their symptoms
3. Use of any investigational drug except for secukinumab during the core study
4. Any subject taking other concomitant biologic immunomodulating agent(s) except secukinumab during the core study

5. Pregnant or nursing (lactating) women, where pregnancy is defined as the state of a female after conception and until the termination of gestation, confirmed by a positive hCG laboratory test.
6. Women of child-bearing potential, defined as all women physiologically capable of becoming pregnant, unless they are using effective methods of contraception during the entire study or longer if required by locally approved prescribing information (e.g., 20 weeks in EU). Effective contraception methods include:
 - Total abstinence (when this is in line with the preferred and usual lifestyle of the subject. Periodic abstinence (e.g., calendar, ovulation, symptothermal, post-ovulation methods) and withdrawal are not acceptable methods of contraception
 - Female sterilization (have had surgical bilateral oophorectomy with or without hysterectomy) or tubal ligation at least six weeks before taking study treatment. In case of oophorectomy alone, only when the reproductive status of the woman has been confirmed by follow up hormone level assessment
 - Male sterilization (at least 6 months prior to screening). For female subjects on the study, the vasectomized male partner should be the sole partner for that subject
 - Barrier methods of contraception: Condom or Occlusive cap (diaphragm or cervical/vault caps) with spermicidal foam/gel/film/cream/ vaginal suppository
 - Use of oral, injected or implanted hormonal methods of contraception or other forms of hormonal contraception that have comparable efficacy (failure rate <1%), for example hormone vaginal ring or transdermal hormone contraception
 - Placement of an intrauterine device (IUD) or intrauterine system (IUS)

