5.5.11 Study completion and post-study treatment

A subject will be considered to have completed the study if he/she received treatment for 260 weeks in the combined core study and extension study (last dose being administered at Week 256) and upon completion of the scheduled study assessments and procedures up to and including Visit F268.

Information on the subject's completion or discontinuation of the study and the reason for discontinuation of the study will be recorded on the appropriate Study Phase Completion eCRF page.

A Study Phase Completion evaluation (associated with the last visit of the subject's phase of the study: e.g. Week 156, Week 208 or Week 260) must also be performed when a subject prematurely withdraws from the study for whatever reason. In any case, the investigator or site staff must contact IRT as soon as possible to record the subject's study completion (Visit F268) or discontinuation.

The investigator must provide follow-up medical care for all subjects who are prematurely withdrawn from the study, or must refer them for appropriate ongoing care. This care may include initiating another treatment outside of the study as deemed appropriate by the investigator. This treatment may be any non-biologic DMARD. In case of a biologic treatment, a waiting period of 3 months before initiating the treatment is recommended.

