^{*} For all subjects who discontinue or withdraw from the study, the investigator should ensure that the subject completes an end of treatment visit (corresponding to the last visit for the subject's current period of treatment) 4 weeks after last study treatment and also return after an additional 8 weeks for a final follow-up, F268 (12 weeks after last study treatment). The final visit should be performed before any new treatment is initiated.

Table 6-3 Assessment schedule - Part 3: Week 212 to Week 260 and follow-up visit F268

Epoch	Treatment period 5													
Week	212	216	220	224	228	232	236	240	244	248	252	256	260*	F268*
Optional Site Visit ¹	X	X		X	X		X	X		X	X	X		
Physical exam ²			X			X			X				X	
Weight						X							X	
Vital signs			X			X			X				X	
Hematology, blood chemistry, urinalysis			X			X			X				X	
Urine pregnancy test			X			X			X				X	
ECG						X							X	
Administration of study treatment ³	X	X	X	X	X	X	X	X	X	X	X	X		
Conc. Medication/non-drug therapy	Update as necessary													
Adverse events/SAE ⁴	Update as necessary													
Patient's global assessment of disease activity (VAS)			X			X			X				X	
Patient's assessment of spinal pain (VAS)			X			X			X				X	

Epoch	Treatment period 5													
Week	212	216	220	224	228	232	236	240	244	248	252	256	260*	F268*

Lipids ⁷						X							X	
Cardiovascular panel													X	
Treatment period 5 completion form													X	
Follow-up completion form														X

¹ Optional visits – Week 212, 216, 224, 228, 236, 240, 248, 252, 256. At these optional visits only those subjects who are unable to self-administer the PFS injections at home will visit the site and site staff will supervise self-administration or administer the PFS injection for them. Other subjects who can self-administer the PFS injection can do so at home at these optional visits.

² These assessments are source documentation only and will not be entered into the eCRF

³ The study treatment (PFS) has to be administered every 4 weeks. From Week 104E1 to 116, subjects will visit the site every 4 weeks for

Epoch	Treatment period 5													
Week	212	216	220	224	228	232	236	240	244	248	252	256	260*	F268*

administering the PFS injection (by self or by site staff). After Week 116, at visits marked as optional visits, subjects can self-administer the study PFS at home or may visit the site to receive the PFS administration by site staff.

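### Protocol 7.3 ties pregnancy reporting to an undefined on-treatment period with no post-treatment tail, while SAE reporting, adverse event counting and study follow-up run 12 weeks past the last dose

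*Protocol*

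**What the plan says.** Protocol 7.3 requires that "each pregnancy occurring while the subject is on study treatment must be reported to Novartis within 24 hours of learning of its occurrence". The next sentence asks for that pregnancy to be followed to its outcome. The section gives no period after treatment and no definition of being on treatment.

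Other parts of the plan extend past the last dose:

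- Protocol 3.1: "A follow-up visit is to be done 12 weeks after the last study treatment administration for all subjects", whether they complete or stop early.
- Protocol 5.5.11: a completer is someone who "received treatment for 260 weeks in the combined core study and extension study (last dose being administered at Week 256") and who also finishes the procedures up to and including Visit F268.
- Schedule footnotes in section 6: subjects who stop early have an end-of-treatment visit 4 weeks after the last dose and then "return after an additional 8 weeks for a final follow-up, F268 (12 weeks after last study treatment").
- Protocol 7.2: SAEs are reportable regardless of causality to 12 weeks after the last dose, or 30 days after participation stops.
- Protocol 9.5.2 and SAP 16: treatment-emergent adverse events are counted to 84 days after the last dose.

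In Table 6-3 the "Treatment period 5 completion form" is marked at Week 260 and the "Follow-up completion form" at F268. The "Urine pregnancy test" is last marked at Week 260.

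**The concern.** The plan treats the 12 weeks after the last dose as relevant to SAEs, adverse event counts and follow-up, but the pregnancy rule does not mention them. A site that takes 7.3 at its word could learn at F268 of a pregnancy that began after treatment ended and have no duty to report it or follow its outcome. Protocol 10.2, meanwhile, has women told of unknown fetal risk from a pregnancy during the study, and the study includes F268.

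At stake is the completeness of pregnancy safety data: uncomplicated pregnancies, routine outcome follow-up, and late outcomes that nobody links to the drug. Because the term is undefined, sites could also apply the rule differently from one another.

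**Working it through.** **Inputs.** Last dose for a completer: Week 256 (Protocol 5.5.11). End-of-treatment visit: 4 weeks after the last dose, which is Week 260 for a completer (Protocol 5.5.9; Table 6-3). Follow-up visit: 12 weeks after the last dose (Protocol 3.1). Analysis window: 84 days after the last dose (Protocol 9.5.2; SAP 16).

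**The plan's own figure.** 256 + 12 = 268, which matches F268. 84 / 7 = 12 weeks, so the analysis window ends at the same point.

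**Uncovered time.** Gap = end of follow-up minus the end of the on-treatment period.

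| Reading of the on-treatment period | Completer | Early discontinuer, last dose at Week L |
|---|---|---|
| Ends at the last dose | 268 − 256 = 12 weeks | (L + 12) − L = 12 weeks |
| Ends at the end-of-treatment visit | 268 − 260 = 8 weeks | (L + 12) − (L + 4) = 8 weeks |
| Ends 84 days after the last dose | 268 − 268 = 0 weeks | (L + 12) − (L + 12) = 0 weeks |

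**Which reading fits best.** For completers, 5.5.11 counts 260 weeks of treatment, and Table 6-3 closes treatment period 5 at Week 260 with a separate form for follow-up. That favours 8 weeks over 12. For early discontinuers, the glossary places treatment discontinuation at the point where the subject permanently stops taking treatment, and it defines stopping study participation separately. That favours an end at or near the last dose, so a gap of up to 12 weeks. The 84-day reading takes a definition written for analysis and uses it as a site instruction; 7.3 does not refer to it.

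**Search for a rule elsewhere.** Protocol 6.5.7 covers testing, interrupting drug and discontinuing the subject. Protocol 5.5.9.1 lists pregnancy as a reason to stop treatment. Neither adds a reporting period, and the SAP has no pregnancy reporting rule. In the text available, nothing else supplies the missing tail.

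**Detection.** The last scheduled urine test is at Week 260, which is 268 − 260 = 8 weeks before F268. On the schedule, a pregnancy that starts later becomes known only if the subject tells the site. Subjects who withdraw consent are left out, because Protocol 5.5.9.2 allows no further contact.

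**The case against.** The strongest reply is that little is lost in practice.

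- Serious outcomes have other routes. A congenital anomaly is an SAE by definition (7.1), SAEs are reportable in the 7.2 window and later if the investigator suspects the drug, and 7.3 itself sends any SAE in pregnancy to the SAE form. Under 7.1, late events that the subject or the personal physician thinks related must go to the sponsor if serious. This stands and limits the point, but every one of these routes needs an SAE.
- The 24-hour clock starts when the site learns of the pregnancy. One that began on treatment but came to light at F268 is therefore still covered. This also stands: only pregnancies beginning after treatment ends are at issue.
- The second paragraph of 7.3, on the pregnancy form, has no on-treatment qualifier. A site could read it as covering follow-up pregnancies, but it reads most naturally as the procedure for those just described. This adds to the ambiguity and does not settle it.

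Two stronger readings may tempt a reader, and the documents support neither.

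- **That 7.3 contradicts exclusion criterion 6 (Protocol 4.2).** That criterion sets contraception for the whole study, without naming F268. No text says that the reporting period must match it.
- **That reporting must run for any longer local-label period.** Criterion 6 adds "or longer if required by locally approved prescribing information (e.g., 20 weeks in EU"), which from the last dose would reach 256 + 20 = 276, or 276 − 268 = 8 weeks past F268. Criterion 6 does not say where the 20 weeks start; the last-dose anchor is inferred from the Amendment 1 rationale. The labels are outside the documents, and no contact is scheduled after F268. The same rationale says that no evidence shows a specific post-treatment duration to be needed for patient safety, so contraception length is a weak benchmark for reporting.

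**Conclusion.** The point holds as a minor one. Section 7.3 ties the duty to report and follow a pregnancy to a term it does not define, and it gives no post-treatment period where the neighbouring safety rules give 12 weeks. On a literal reading, up to 12 weeks are uncovered for early discontinuers and 8 to 12 weeks for completers, with 8 the better supported figure for completers. The gap is zero only if the 84-day analysis window is read in.

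The size in subjects cannot be stated: the documents give neither the number of women of child-bearing potential nor a pregnancy rate. No planned analysis is affected, and the safety objective in Protocol 2.2 runs to Week 260. It would be wrong to infer that serious pregnancy outcomes go unreported as a rule.

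**What to change.** In Protocol 7.3, replace the on-treatment qualifier with: *from the first dose of study treatment until 12 weeks after the last dose (F268)*. This matches the 12-week limb of 7.2 and the follow-up visit, and it removes a judgement that sites could make differently.

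An extension to a longer contraception period under local prescribing information is optional and not part of the required change. It would depend on subjects volunteering the information after F268.

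The cost is one wording change in a protocol amendment, plus a few additional pregnancy reports and their follow-up. No visit, test or analysis is added.
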